## III. STUDY DESIGN

### Study Period

July 1, 2020 to October 25, 2020 (the date of data pull)

[figure not shown]
The start date is when all hospital sites started using the same ERH management system. The study period end date is October 25, 2020 with last convalescent plasma administration occurring 28 days prior on September 27, 2020.

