### Cohort Sampling

This is a retrospective cohort study with risk-set sampling for exposure status of convalescent plasma using EHRs in the Baylor Scott & White Health (BSWH) healthcare delivery system. In brief, patients who received convalescent plasma will be matched to a similar population who did not receive convalescent plasma around the same time ( $\pm 2$  days) of transfusion across sites. The administration date of convalescent plasma for the treated population and the matched date for the untreated population are thereafter referred as the index date. The matching scheme for risk-set sampling is defined in step-by-

step points in the following paragraph. The follow-up for the matched cohort will start from the index date and continue until the end of the observation period. The observation period for this study is defined as at least 28 days from the index date. In other words, the index date must be at least 28 days prior to the date of data pull to allow for adequate follow-up and minimize selection bias from informative censoring due to death or discharge for palliative care. An unexposed patient at the index date could receive convalescent plasma during the follow-up and the follow-up will be censored at the administration date of convalescent plasma (Figure 1).

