**Figure 1. Schematic diagram for retrospective cohort study with risk-set sampling for convalescent plasma exposure**

CP= convalescent plasma

\* Hospital admission includes the earliest encounters at emergency or inpatient departments around COVID-19 confirmation within  $\pm 14$  days.

† The earliest possible date is July 1st, 2020.

Step-by-step risk-set sampling with replacement for the retrospective cohort design to account for confounding and to strategize EHR abstraction at BSWH:

1. Identify patients hospitalized with laboratory-confirmed COVID-19 (Source population)

The study population will be patients with laboratory-confirmed COVID-19 (i.e., RT-PCR test results recorded by the BSWH laboratory informatics systems and/or the EHR system) and received or matched to a patient who received convalescent plasma from July 1st to September 28th. Patients must have at least 28 days of observation opportunity from the date of data pull to the index date (reverse order). Patients cannot have been previously admitted into hospitals due to RT-PCR laboratory confirmed COVID-19.

2. Identify patients who received convalescent plasma (Exposed group)

Blood bank records will be scanned to identify patients who had at least one order to transfuse COVID-19 convalescent plasma using the International Society of Blood Transfusion (ISBT) 128 codes (Appendix 1). The order will be linked to the administration record of the plasma to determine the date and time the product was given.

3. Risk-set sampling and matching variables (Unexposed group)

For each patient who received a first dose of convalescent plasma, we will sample from the source population who did not receive convalescent plasma (Unexposed group) at the same calendar time ( $\pm 2$  days) and match on the following variables. One patient could be sampled at maximum twice; first sampled into the unexposed group and later sampled into the exposed group due to initiation of convalescent plasma transfusion during follow-up.

- Calendar date around the index date within  $\pm 2$  days: Risk-set sampling to match exposed and unexposed patients will account for this factor
- Age ( $\pm 5$  years)
- Sex (female, male)
- Days from hospital admission to the index date

4. Propensity score matching and baseline covariates

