### Study Outcomes

- Safety

Safety events related to plasma transfusion were selected from the Centers for Disease Control and Prevention (CDC) National Healthcare Safety Network (NHSN) Biovigilance Component Hemovigilance Module Surveillance Protocol.a The following safety outcomes will be identified by ICD-10-CM billing codes (Appendix 5).

- Transfusion associated circulatory overload (TACO)
- Transfusion-related acute lung injury (TRALI)
- Anaphylactic reaction

---

a The following events were excluded because they are irrelevant for plasma transfusion or because there are no transfusion-specific billing codes. Transfusion-associated graft vs. host disease (TAGVHD) is associated with a cellular product. Delayed hemolytic transfusion reaction (DHTR) and delayed serologic transfusion reaction (DSTR) are associated with red cells containing products. Post transfusion purpura (PTP) is associated with platelets containing products. No transfusion specific billing codes exist for transfusion-associated dyspnea (TAD) allergic reaction and hypotensive transfusion reaction.

- Febrile non-hemolytic transfusion reaction
- Transfusion-transmitted infection
- Acute hemolytic transfusion reaction
- A composite outcome of thrombotic or thromboembolic complication including stroke, myocardial infarction, venous thromboembolism, deep vein thrombosis, and pulmonary embolism
- A composite outcome of cardiac arrhythmias including ventricular tachycardia, ventricular fibrillation, atrial arrhythmia, and cardiac arrest
- Effectiveness
  - Primary:
    - 28-day in-hospital mortality
  - Secondary:
    - Discharge alive
    - ICU transfer
    - Mechanical ventilation

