## **IV. STATISTICAL ANALYSIS PLAN**

### **All patients**

#### Descriptive Analyses

We will describe distribution of baseline covariates (Appendix 2), including demographics, comorbidities, concomitant medications, and severity measures of COVID-19 for the exposed and unexposed groups. The number of patients, mean, standard deviation, median, interquartile range, and range will be presented for continuous variables, and counts and percentages of patients in each category will be presented for categorical variables.

Given the modest sample size and rarity of the safety outcomes, we will explore the occurrence of safety outcomes, and present counts and percentages.

The crude incidence rates of death in the first 7, 14, 21, and 28 days after the index date will be estimated for the exposed and unexposed groups using the cohort before propensity score matching.

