### Sensitivity Analyses

- 1) To assess the COVID-19 cohort definition of hospital admission within ±14 days of laboratory confirmed COVID-19 diagnosis, we will further restrict the source population to those who were admitted into affiliated BSWH hospitals within ±7 days of laboratory confirmed COVID-19 diagnosis. This is because COVID-19 could progress quickly and patients could also transfer to hospitals outside of the network of BSWH with a large time window around COVID-19

confirmation resulting in potential residual confounding by severity and survivor bias by prior treatment

- 2) Instead of ending the observation period at 28 days since the index date, we will continue follow-up until the end of the study period, unless an outcome event occurs earlier. Patients will be followed from the index date until the earliest of the following: 1) death, 2) discharge alive, 3) the end of the study period, or 4) the date of unexposed patients who were administrated COVID-19 convalescent plasma.
- 3) Given that mortality data after hospital discharge is limited and that patients could be discharged for palliative care due to disease worsening, the outcome “discharge alive” will be considered a competing risk for 28-day in-hospital mortality. To account for competing risk of in-hospital death and discharge alive, sub-distribution hazard ratios will be estimated from the Fine-Gray model. Cumulative incidence function will be estimated by modeling the cause-specific hazard function of all causes.

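### Safety events rest on billing codes alone, and the stated data pull falls on day 28 for the last recipients, so safety percentages may be somewhat low

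*Protocol*

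**What the plan says.** Four statements in the protocol bear on this.

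- **Source of events.** Study Outcomes: "The following safety outcomes will be identified by ICD-10-CM billing codes (Appendix 5". No second source is named. A footnote there says that some reactions were left out because no transfusion-specific code exists for them.
- **Timing.** Study Period gives the window as "July 1, 2020 to October 25, 2020 (the date of data pull" and adds: "The study period end date is October 25, 2020 with last convalescent plasma administration occurring 28 days prior on September 27, 2020".
- **Entry rule.** Cohort Sampling: "the index date must be at least 28 days prior to the date of data pull to allow for adequate follow-up". There is no condition on discharge or on completed coding.
- **Reporting.** Descriptive Analyses: "we will explore the occurrence of safety outcomes, and present counts and percentages". No person-time and no rule for incomplete records is given.

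The second sensitivity analysis shows that stays beyond day 28 are foreseen: "Instead of ending the observation period at 28 days since the index date, we will continue follow-up until the end of the study period".

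**The concern.** A 28-day minimum gap between index date and pull suits outcomes such as death and discharge. It does not suit an outcome that exists only once a stay has been coded. If coding is completed after discharge, a patient still in hospital at the pull, or discharged shortly before it, can show no safety event whatever happened. That patient has nevertheless entered the cohort on 28 days of opportunity alone.

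At stake is the description of safety under primary objective (ii). The error runs in one direction, towards fewer reported events, and Descriptive Analyses itself calls these outcomes rare, so a few missed events would be visible. The validation under Data Sources (10-20 records per data point against chart review) tests the extraction script. It is not designed to show whether coding was complete at the pull.

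**Working it through.** **Dates.** October 25 minus 28 days is September 27, which reproduces the Study Period statement. The slack between day 28 of the last recipients and the pull is 28 - 28 = 0 days. The source-population step under Cohort Sampling gives another end date ("received or matched to a patient who received convalescent plasma from July 1st to September 28th"). On that date the gap is 27 days, so the slack is -1 day. The earliest index date, July 1, has 116 days to the pull. The problem therefore sits with late index dates and long stays.

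**Size: assumptions, none of them in the protocol.** Index dates are even over July 1 to September 27 (89 days). Stay after index is lognormal with median m = 7 or 10 days and a share p = 4% or 13% beyond day 28. Codes become available a fixed lag L after discharge.

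For F = 28 to 116 days from index to pull:

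- σ = ln(28/m) / z(1-p), with z = 1.751 for 4% and 1.126 for 13%. For m = 7 this gives 1.386/1.751 = 0.792 and 1.386/1.126 = 1.231. For m = 10 it gives 1.030/1.751 = 0.588 and 1.030/1.126 = 0.914.
- Share uncoded at F = 1 - Φ[(ln(F - L) - ln m)/σ], set to 1 when F ≤ L. The average over F is the share of all patients.

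Example, last index day, m = 10, p = 13%, L = 14: (ln 14 - ln 10)/0.914 = 0.368, so 1 - Φ(0.368) = 35.6%.

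Results across the four combinations of m and p:

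| Lag L | All patients | Index dates in last 28 days |
|---|---|---|
| 0 days | 0.4-4.1% | 1.2-7.9% |
| 7 days | 1.0-5.2% | 2.9-10.6% |
| 14 days | 2.1-7.0% | 6.1-15.9% |
| 30 days | 13.6-19.5% | 41-52% |

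**Cross-check.** With exponential stays, the share of all patients is the mean of exp[-(ln 2/m) × max(F - L, 0)]. For medians of 7-10 days and lags of 0-14 days this gives 0.7-6.3%. A median of 14 days with a 14-day lag gives 11.5%, so the answer depends on the assumed stay as well as the lag.

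**Later reading of the codes.** The protocol is dated November 10, 16 days after the pull. If codes were read that day, F rises by 16. The 0-14 day rows fall to 0.1-3.8% of all patients, and the 30-day row falls to the 14-day row (30 - 16 = 14).

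**Effect on a percentage.** Take an illustrative true risk of 5% and a share q of stays uncoded. If those stays carry the same risk, the reported figure is 5% × (1 - q): 4.98% at q = 0.4% and 4.65% at q = 7%. If they carry three times the risk, it is 5% × (1 - q)/(1 + 2q): 4.94% and 4.08%.

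**The case against.** The strongest reply is that October 25 may be only an observation cut-off. The protocol is dated November 10 yet still describes extraction, script validation and the data-element table in Appendix 4 as work to come. That fits code fields being queried later. It is not decisive, because Study Period calls October 25 the date of the pull and names no other, but it makes the point conditional.

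Other parts of the reply also stand:

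- Coding after discharge, and any lag, are general knowledge about billing data and not protocol text.
- A full-cohort denominator is the plain reading of Descriptive Analyses, not a written rule.
- Safety is to be described, not tested.

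A reader might infer three stronger things that the document does not support:

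- **That the comparison between groups is biased.** Matching on calendar date within ±2 days gives both groups nearly the same time to the pull. Distortion arises only if their lengths of stay differ.
- **That a fifth of patients, or half of the late ones, are lost.** That needs a lag of about 30 days, which nothing in the protocol supports.
- **That all the listed complications cluster in the longest stays.** The protocol does not say so, and anaphylactic, febrile and acute hemolytic reactions follow a transfusion rather than the length of stay.

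What remains is that source, pull date and entry rule, followed as written, admit patients whose outcome field may still be empty. No later analysis plan can recover codes that are absent from the extract.

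**Conclusion.** The point holds in conditional form. If the codes are read at the stated pull, and if they are completed after discharge, some late and long stays add no safety events while remaining in the denominator, and the descriptive percentages come out somewhat low. For medians of 7-10 days, 4-13% of stays beyond day 28 and lags of 0-14 days, this concerns about 0.4-7% of patients and about 1-16% of those indexed in the last 28 days. All figures shrink if the codes were in fact read after November 10. The main effect is under-counting. The effectiveness outcomes are not defined through the Appendix 5 codes and are not affected. This is a worthwhile, inexpensive improvement to the safety description, not a threat to the primary result.

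**What to change.** State that October 25, 2020 is the cut-off for observation. Extract the ICD-10-CM fields for the fixed cohort again once its encounters are closed and final-coded, and leave the effectiveness data as pulled. The cost is one repeat query and a short delay to the safety tables.

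If no second extraction is possible:

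- Keep the full-cohort safety table.
- Report by group how many encounters were open or uncoded at the pull.
- Add a sensitivity table limited to index dates early enough that nearly all stays are coded. Dropping the last 28 of the 89 index days, for example, leaves at a 14-day lag between (89 × 2.47 - 28 × 7.57)/61 = 0.1% and (89 × 7.01 - 28 × 14.92)/61 = 3.4% uncoded under the assumptions above.

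Do not restrict instead to final-coded encounters. That would remove the longest stays and bring in a selection of its own.

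The two end dates for plasma administration, September 27 in Study Period and September 28 in the source-population step, should be reconciled at the same time.

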### **Covariates**

Covariates including those for risk-set sampling and propensity score matching (See Cohort Sampling) will be assessed during baseline and are listed in Appendix 2. Baseline is defined as the period prior to and including the index date. For variables (e.g., vital signs and comedications) assessed at multiple time points, the value closest to the index date will be used. However, for oxygenation, the worst measures 4-12 hours prior to the index date will be used. For variables (e.g., cardiovascular conditions) that are usually collected at hospital admission or possibly in previous healthcare encounters for other health concerns, the value will be searched in the past year from and including the hospital admission date, unless specified otherwise. The lookback period for each covariate is listed in Appendix 2.

## **IV. STATISTICAL ANALYSIS PLAN**

### **All patients**

#### Descriptive Analyses

We will describe distribution of baseline covariates (Appendix 2), including demographics, comorbidities, concomitant medications, and severity measures of COVID-19 for the exposed and unexposed groups. The number of patients, mean, standard deviation, median, interquartile range, and range will be presented for continuous variables, and counts and percentages of patients in each category will be presented for categorical variables.

Given the modest sample size and rarity of the safety outcomes, we will explore the occurrence of safety outcomes, and present counts and percentages.

The crude incidence rates of death in the first 7, 14, 21, and 28 days after the index date will be estimated for the exposed and unexposed groups using the cohort before propensity score matching.

#### Comparative Analyses

A Kaplan-Meier curve will be plotted using the propensity score matched cohorts. To control for measured confounding, patients will be sampled in risk sets with replacement and propensity score matched. Distribution of covariates between exposure groups before and after propensity score matching will be assessed to evaluate the balance of baseline covariates and potential residual confounding. Absolute standardized differences, the differences in means or proportions divided by the pooled standard deviation, will be computed for each covariate to check its distribution balance within exposure groups. Covariates with an absolute standard difference greater than 0.1 will be further controlled in the analyses by including specific variables in the Cox model.

The adjusted incidence rates of death in the first 7, 14, 21, and 28 days after the index date will be estimated for the exposed and unexposed groups using the propensity score-matched cohort.

For the primary outcome (28-day in-hospital mortality), a Cox proportional hazards regression will estimate hazards ratios (HRs) and 95% confidence intervals (CIs) using the propensity score-matched cohort. Patients will be followed from the index date until the earliest of the following: 1) death, 2) discharge alive, 3) day 28 since the index date, or 4) the date of unexposed patients who were administered COVID-19 convalescent plasma. Patients discharged alive will be censored at the discharge date. The proportional hazards assumption will be evaluated using Schoenfeld residuals test and visual inspection of log-log plots.

For the secondary outcome of discharge alive, we will not censor the follow-up at the date of in-hospital death but will censor at day 28 to account for this worst possible outcome and to account for the competing risk of in-hospital death. In other words, patients will be followed from the index date until the earliest of the following: 1) discharge alive, 2) day 28 since the index date, or 3) the date of unexposed patients who were administered COVID-19 convalescent plasma.

A Cox proportional hazards regression will estimate HRs and 95% CIs using the propensity score-matched cohort for the secondary outcomes of ICU transfer and mechanical ventilation. Patients will be followed from the index date until the earliest of the following: 1) the outcome of interest, 2) death, 3) discharge alive, 4) day 28 since the index date, or 5) the date of unexposed patients who were administered COVID-19 convalescent plasma.

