## II. OBJECTIVES

### A. PRIMARY OBJECTIVES

- (i) To estimate the relative risk of effectiveness outcomes of interest in laboratory confirmed COVID-19 patients who received convalescent plasma compared with COVID-19 patients who did not receive convalescent plasma.
- (ii) To describe safety outcomes of interest in laboratory confirmed COVID-19 patients who received convalescent plasma compared with COVID-19 patients who did not receive convalescent plasma.

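### The primary mortality analysis censors live discharges and its only outcome curve is Kaplan-Meier, so neither the curve nor the Cox hazard ratio gives the 28-day in-hospital risk or relative risk that the protocol targets

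*Protocol*

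**What the plan says.** The primary effectiveness outcome is "28-day in-hospital mortality" (Protocol, Study Outcomes). The first primary objective is stated on the relative-risk scale: "To estimate the relative risk of effectiveness outcomes of interest in laboratory confirmed COVID-19 patients" (Primary Objectives). Section V also expresses its detectable effects as relative risks.

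Under Comparative Analyses, "a Cox proportional hazards regression will estimate hazards ratios (HRs) and 95% confidence intervals (CIs) using the propensity score-matched cohort". Follow-up stops at live discharge, and "Patients discharged alive will be censored at the discharge date". The same section says "A Kaplan-Meier curve will be plotted using the propensity score matched cohorts". That sentence names neither an outcome nor a censoring rule. Rates of death at days 7, 14, 21 and 28 are listed as a separate item, with no estimator given.

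For the secondary outcome of discharge alive, the section takes the opposite approach to the event that precludes it: "we will not censor the follow-up at the date of in-hospital death but will censor at day 28", the reason being "to account for this worst possible outcome and to account for the competing risk of in-hospital death".

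Sensitivity analysis 3 then says that discharge alive "will be considered a competing risk for 28-day in-hospital mortality". It plans a Fine-Gray model and a cumulative incidence function built from the cause-specific hazards of all event types.

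**The concern.** In-hospital death and live discharge exclude each other, and the protocol recognises this in two places. Yet the primary analysis of death treats discharge as ordinary censoring, while the secondary analysis of discharge treats death as competing. No reason is given for the difference.

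Two things are at stake. First, if the Kaplan-Meier curve follows the stated mortality rule, reading one minus the curve as a risk assumes that discharged patients would go on dying in hospital at the rate of those still there. They cannot, so the curve ends too high in both groups. Second, the Cox model compares death rates among patients still in hospital. The 28-day risk also depends on how fast patients leave. If plasma changes the speed of discharge, which the protocol studies as a secondary outcome, the hazard ratio and the 28-day risk ratio can part company. The headline estimate would then not answer the stated objective.

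**Working it through.** **1. The protocol's own target scale.** Inputs from Section V: 28-day survival 0.75, 80% power, two-sided 0.05, log-rank test with Freedman's tables as reference. Write φ for the ratio of plasma to comparator patients.

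- Events required: (1.960 + 0.842)² × (1 + φ·HR)² / [φ(1 − HR)²]
- Events expected: n(plasma) × (1 − 0.75^HR) + n(comparator) × 0.25

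For 1,000 patients at 1:1, HR = 0.678 balances the two: 7.849 × 1.678² / 0.322² ≈ 214, and 500 × 0.177 + 125 ≈ 214. The corresponding risk ratio is 0.177/0.25 = 0.71, the figure in Table 1. For 2,500 at 1:4, HR = 0.728 and the risk ratio is 0.76, again as printed. All 16 rows reproduce as risk ratios. Read as a hazard ratio, the first row would be 0.68, not 0.71. So the plan is powered for a 28-day risk ratio.

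**2. The curve.** Assume constant hazards, d for death and r for live discharge, per day.

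- True in-hospital risk by day 28: d/(d + r) × [1 − exp(−28(d + r))]
- One minus Kaplan-Meier with discharge censored: 1 − exp(−28d)

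The 25% mortality carries Section V's all-cause figure over to in-hospital death. That is an assumption, and so are the discharge shares. If p die, q are discharged and 1 − p − q remain at day 28, then d + r = −ln(1 − p − q)/28 and d = (d + r) × p/(p + q). Worked case, q = 0.65: d + r = −ln(0.10)/28 = 0.0822, d = 0.0822 × 0.25/0.90 = 0.0228, and 1 − exp(−28 × 0.0228) = 0.47.

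| Discharged alive by day 28 | True risk | One minus Kaplan-Meier | Ratio |
|---|---|---|---|
| 30% | 25% | 30% | 1.22 |
| 50% | 25% | 37% | 1.48 |
| 60% | 25% | 43% | 1.71 |
| 65% | 25% | 47% | 1.89 |
| 70% | 25% | 55% | 2.18 |

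Timing matters too. Simulating gamma-shaped event times at 25% mortality and 50-70% discharged gave ratios from 1.34 (50% discharged, deaths earlier than discharges) to 3.04 (70% discharged, discharges much earlier than deaths). The ratio exceeded 1 in every scenario.

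**3. The hazard ratio.** Take d = 0.03 and r = 0.09 per day in the comparator group. The 28-day risk is 0.25 × (1 − exp(−3.36)) = 0.241. Leave d unchanged, so the cause-specific hazard ratio is exactly 1.0, and let plasma multiply r:

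| Discharge-rate ratio | 28-day risk with plasma | Risk ratio |
|---|---|---|
| 0.7 | 0.03/0.093 × (1 − exp(−2.604)) = 0.299 | 1.24 |
| 0.8 | 0.03/0.102 × (1 − exp(−2.856)) = 0.277 | 1.15 |
| 1.25 | 0.03/0.1425 × (1 − exp(−3.99)) = 0.207 | 0.86 |

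With 25% mortality and 65% discharged in the comparator group, the same three ratios give 1.19, 1.12 and 0.88.

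**4. Would keeping discharged patients at risk to day 28 repair it?** Unexposed patients are also censored when they receive plasma. A discharged patient can no longer cross over, so under that rule discharged patients stay in the unexposed risk set in full while those still in hospital are depleted. With the hazards of step 3, no true difference between groups, and an assumed crossover rate of 0.01 to 0.03 per day (about 7% to 20% crossing over), the apparent unexposed risk falls from 24.1% to 23.4% and 22.2%. That is a spurious risk ratio of 1.03 to 1.09 against plasma. A Fine-Gray model with censoring weights avoids this; the simple rule does not.

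**The case against.** The strongest reply is that a Cox model that censors a competing event is a recognised analysis. It estimates the cause-specific hazard ratio and needs no assumption about what happens to discharged patients. A reader might infer that the primary hazard ratio is biased or invalid. The documents do not support that: it is a sound measure of the in-hospital death rate. The subdistribution hazard ratio is no relative risk either. At 25% mortality, 65% discharged and a discharge-rate ratio of 0.7, it is 1.22 where the risk ratio is 1.19. Making Fine-Gray primary would therefore be a trade-off, not a correction.

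A reader might also infer that the protocol ignores the problem. It does not. Sensitivity analysis 3 plans the right tools, Cohort Sampling mentions informative censoring through palliative discharge, and Limitations plans an intent-to-treat analysis with fixed follow-up, though that one addresses treatment switches and transfers.

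Finally, a reader might state a twofold overstatement as fact. The documents give no discharge share or length of stay. Under constant hazards at 25% mortality, a ratio near two needs roughly 65-70% discharged. That the curve censors discharges is itself an inference from the mortality follow-up rule.

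What still stands is the mismatch. The objective and the sample size are on the 28-day risk scale, and the main analysis specifies no estimate on that scale that allows for discharge.

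**Conclusion.** The point holds as a mismatch between target and primary analysis. If the Kaplan-Meier curve follows the stated mortality rule, it will overstate 28-day in-hospital mortality. The direction is certain once anyone is discharged before later deaths occur. The size is not: 1.2 to 2.2 times at 25% mortality with constant hazards and 30-70% discharged, and up to about 3 times in the simulated timings with early discharge. The Cox hazard ratio is valid as a cause-specific measure, but it can equal 1.0 while the day-28 risk ratio lies between 0.86 and 1.24, for assumed discharge-rate ratios of 1.25 down to 0.7. The discharge shares, hazards and discharge effects are all assumptions. The fault is one of ranking and labelling: the analysis that matches the objective is planned, but only as a sensitivity analysis.

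**What to change.** In Comparative Analyses:

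- Replace the Kaplan-Meier curve with cumulative incidence curves for in-hospital death, with live discharge as the competing event.
- Report the risks at days 7, 14, 21 and 28, with the risk difference and risk ratio, from those curves as main results. This moves the cumulative incidence function of sensitivity analysis 3 into the main analysis.
- Keep the Cox hazard ratio, label it cause-specific, and report it beside the hazard ratio for discharge alive and the planned Fine-Gray estimate. As planned, the discharge outcome keeps deaths at risk, so say which type of hazard ratio it is.
- Do not simply keep discharged patients at risk to day 28. Given censoring at crossover, that is not equivalent to Fine-Gray and lowers the unexposed risk unless censoring weights are used.

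The cost is a wording change and slightly more reporting. No new data are needed, and the methods are already planned, although the protocol does not say that they are programmed. One limit remains: the risks still cover in-hospital death only, so deaths after discharge, including after palliative discharge, are not counted.
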